### **9.6.2 Patient Satisfaction using a 5-point Likert Scale**

Patient satisfaction assessment will be performed independently by the subject using pre-defined scale questionnaire. The subjects will answer this questionnaire at each follow-up visit (6wk FU, and 12wk FU).

### **9.6.3 Investigator Satisfaction using the Clinical Global Aesthetic Scale**

Satisfaction assessment will be performed by the study investigator using a pre-defined scale questionnaire. The investigator will answer this questionnaire at each follow-up visit (6wk FU, and 12wk FU)

### **9.6.4 Pain Rating Scale**

The subjects will rate their pain at the treatment visit.

### **9.6.5 Abdominal Fat Thickness Measurements**

Abdominal fat thickness will be assessed at the treatment area prior to starting the treatment and following the treatment.

## 10 PATIENT COMPLETION / WITHDRAWAL

### 10.1 Completion

A subject will be considered to have completed the study if they complete the treatment as well as both follow up visits.

### 10.2 Withdrawal from the study

A subject will be withdrawn from the study for any of the following reasons:

- Withdrawal of consent
- Subject is not compliant with requirements of the study, including inclusion and exclusion criteria.
- The investigator believes that for safety reasons (e.g. an adverse event) it is in the best interest of the patient to stop the study.
- The study is prematurely stopped or halted (e.g. clinical halt)

Subjects enrolled in the study can discontinue their participation at any time for any reason without prejudice or reduction in the quality of their medical care. The investigators or sponsor can terminate a subject's participation in this study to protect the subject's health or if the subject fails to follow directions resulting in noncompliance to study procedures. Subjects who fail to complete the study will be replaced and will not be considered evaluable.

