### 5.4 Safety Endpoint

Number, severity and type of adverse events recorded throughout the study and post treatment phase (immediate and delayed response), including skin reactions (erythema, edema, irritation, etc.).

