### **6.3 Informed Consent**

Written informed consent will be obtained from each study patient prior to enrollment into the study. A written informed consent (approved by BeShape Technologies Ltd. and the Ethics Committee) must be signed and dated by the patient (or legally authorized representative, if appropriate), and the investigator. Patients will be given a copy of the signed informed consent document. The signed informed consent will be retained with the study records at the site. It is the responsibility of the Investigator to assure that informed consent is obtained from each patient in accordance with GCP guidelines. Subjects may withdraw their consent to participate in the study at any time without prejudice. The investigator may withdraw a subject if, in his clinical judgement, it is in the best interest of the subject or if the subject cannot comply with the protocol.

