## **8 ADMINISTRATION OF TREATMENT**

Subjects will receive one treatment with the BeShape One™ device on the anterior abdomen. Prior to the treatment, measurements of weight and waist circumference will be performed.

Before starting the procedure using the BeShape One™ device, the administrator should clean the entire treatment area with a wet wipe and hairs should be shaved. Conductive castor oil will be applied to the treatment areas to ensure full contact between the applicator and the skin. Prior to treatment, it is necessary for the operator to ensure that all treatment areas are in close contact with the cup-shaped applicator chamber. Following visual confirmation of proper contact with the tissue, the skin will be marked as a

treatment area using a skin marking pen. Subjects will receive treatment on at least 4 abdomen/flanks treatment areas and up to 6 treatment areas, at the discretion of the investigator. During the procedure, subjects will lie in the supine position in order to provide the best access to the treatment area.

Upon completion of treatment, the treated area will be freed from the applicator. The administrator should check for any immediate skin reaction and record any outstanding findings on the CRF before proceeding to the next area of treatment.

Immediately after completion of the procedure (after all treatment areas have been treated), the following evaluations and measurements will be performed:

- \* Assessment of adverse events, including any skin reaction (erythema, edema, irritation, etc.) or any other side effects;
- \* Pain assessment.

All findings will be recorded on the Adverse Events form.

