### **9.4 Treatment**

A single treatment will be administered at the baseline visit, following completion of baseline measurements and photographs. Clinical and safety assessments will be administered prior to and following the treatment.

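### Section 10.2 offers only withdrawal from the study, so a safety or non-compliance decision after the single treatment ends follow-up, with no provision for data still to be collected

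*Combined protocol and SAP*

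**What the plan says.** Section 9.4: "A single treatment will be administered at the baseline visit, following completion of baseline measurements and photographs". The synopsis puts the session at about 1 hour, and Section 9.5 places the two follow-up visits at weeks 6 and 12.

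Section 10.2 opens its list with "A subject will be withdrawn from the study for any of the following reasons". The list covers withdrawal of consent, non-compliance with study requirements, premature stopping of the study, and the safety case: "The investigator believes that for safety reasons (e.g. an adverse event) it is in the best interest of the patient to stop the study". The section ends: "Subjects who fail to complete the study will be replaced and will not be considered evaluable". Section 10.1 defines completion as the treatment plus both follow-up visits.

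Section 6.3 puts the same decision permissively: "The investigator may withdraw a subject if, in his clinical judgement, it is in the best interest of the subject". The closing paragraph of 10.2 is also permissive.

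The safety endpoint in Section 5.4 reads "Number, severity and type of adverse events recorded throughout the study and post treatment phase (immediate and delayed response" and goes on to name skin reactions. Section 11.2.1 sets the primary endpoint as change in waist circumference from baseline to week 12. Section 11.5.1 keeps all treated subjects in the safety set. Section 11.5.2 limits the full analysis set (FAS) to eligible treated subjects with at least one waist measurement after treatment.

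**The concern.** After the treatment session the remaining study activity is assessment: waist, questionnaires, fat thickness, photographs and adverse event review. A decision to withdraw a treated subject at that stage does not limit exposure to the device. It removes the subject from the visits that supply the primary endpoint and the delayed part of the safety endpoint.

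The subjects affected are not a random subset. They leave because of how they tolerated the treatment or because they did not comply, and 10.2 then replaces them with subjects who need share neither problem. With one arm there is no control group in which a similar loss could be seen. At stake are the later course and resolution of the events that led to withdrawal, any new delayed events in those subjects, and their week 12 waist values.

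**Working it through.** **1. What withdrawal changes, by its timing.** Sections 7 and 8 schedule waist measurement before treatment and at the two follow-up visits; the checks straight after the procedure are adverse events and pain only. The first scheduled waist value after treatment is therefore at week 6.

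| Withdrawal occurs | Device exposure avoided | Prompting event in safety set | In FAS | Week 12 waist | Adverse event follow-up lost |
|---|---|---|---|---|---|
| During the session | Remaining areas | Yes, if partial treatment counts as treatment | No | Missing | From the session on |
| After the session, before week 6 | None | Yes | No, absent an unscheduled measurement | Missing | From withdrawal on |
| Between weeks 6 and 12 | None | Yes | Yes | Missing | From withdrawal on |

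The first row exists because several areas are treated in turn: "Subjects will receive treatment on at least 4 abdomen/flanks treatment areas and up to 6 treatment areas, at the discretion of the investigator". Section 8 has the skin checked before the next area is started.

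**2. What the documents provide after withdrawal.** Section 12.1 starts adverse event collection at consent but gives no end and no rule for withdrawn subjects. Section 12.4.2 asks for a resolution date, with no stated procedure to obtain it once a subject has left. Section 11.6.2 lists discontinued subjects with reasons. Section 11.6.4 is descriptive and states no method for missing values.

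**3. Passages that do not agree.**
- Withdrawal is mandatory in the list in 10.2, but permissive in 6.3 and in the last paragraph of 10.2.
- Under 10.1 and 10.2 a subject who leaves between weeks 6 and 12 is not evaluable; under 11.5.2 the same subject, if eligible and measured at week 6, belongs to the FAS.
- Under 10.2 any non-completer is not evaluable; under 11.5.1 every treated subject counts for safety.

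**4. Size.** The one related figure in the plan is 70 subjects (Sections 6 and 11.4). It comes without alpha, power, effect, standard deviation or dropout, so it cannot be reproduced; the point does not depend on it. Everything below rests on assumed values.

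*Replacement.* If 70 is read as the number of completers, enrolment needed is 70/(1 − w), rounded up, where w is the share withdrawn:
- w = 3%: 70/0.97 = 72.2, so 73
- w = 5%: 70/0.95 = 73.7, so 74
- w = 10%: 70/0.90 = 77.8, so 78
- w = 15%: 70/0.85 = 82.4, so 83

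*Mean waist reduction.* Let D be the completers' mean reduction minus that of the withdrawn. The mean over all treated is the completers' mean minus w × D, so the completers' mean is off by w × D. At D = 1 cm this is 0.03, 0.05, 0.10 and 0.15 cm for the four values of w; at D = 2 cm it doubles. D may have either sign. In particular, a subject withdrawn for changing diet or exercise could have a larger waist reduction than completers.

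*Later events not seen.* With m subjects withdrawn, each with chance q of a later event, the chance of missing at least one is 1 − (1 − q)^m:
- m = 2 (about 3% of 70): 1 − 0.90² = 19% at q = 10%; 1 − 0.75² = 44% at q = 25%
- m = 7 (10% of 70): 1 − 0.90⁷ = 52% at q = 10%; 1 − 0.75⁷ = 87% at q = 25%

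**The case against.** A reader might infer that every subject with an adverse event is removed. The text does not say so. The safety trigger is the investigator's belief about the patient's interest, with an adverse event only as an example, and Section 6.3 leaves the decision open. A mild skin reaction would not by itself lead to withdrawal.

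A reader might also infer that the incidence of adverse events will be understated as a direct result. That does not follow either. A subject withdrawn for an event already counts as having one, and the denominator is all treated subjects. Only later or new events can go unseen.

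Nor is it right that withdrawal never spares the subject anything. An event can arise mid-session, and inclusion criterion 7 (no change in diet, exercise or medication) runs for the whole study, so leaving ends that restriction.

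Further, Section 11.6.5 has serious events discussed subject by subject, and Section 12.4.1 refers to sponsor procedures that are not part of these documents and may require follow-up of open events. Silence in the protocol does not prove that data will be lost. The word used in 10.2 for subjects who count is not tied to any analysis set in Section 11, and the likely effect on the mean waist change is modest.

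All of this narrows the point but does not remove it. The mandatory wording remains, non-compliance needs no safety judgement at all, and nothing in the protocol says that any assessment continues after withdrawal.

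**Conclusion.** The point holds in this form: 10.2 makes leaving the study the only kind of discontinuation, applies it to non-compliance and to the investigator's safety judgement, and provides for no later data on treated subjects. After the session this gains nothing in device exposure and costs the week 6 and week 12 assessments still outstanding. Withdrawal before any waist measurement after treatment also takes the subject out of the FAS.

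The size is unknown, because the documents give no adverse event, withdrawal or non-compliance rates. On the assumed values shown, the error in the mean waist reduction is 0.03 to 0.15 cm per 1 cm difference, small and of uncertain direction. The stronger reason to act is safety: even a few withdrawals leave a real chance that a delayed or persisting event is never recorded. This should be changed; it does not by itself invalidate the study.

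**What to change.** In Section 10.2:

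- Separate stopping the treatment session from ending data collection.
- State that treated subjects who are non-compliant, or who stopped for safety, are still asked to attend the planned week 6 and week 12 waist and adverse event assessments, unless they withdraw consent or the investigator judges attendance not to be in their interest. The investigator's clinical judgement and the care of the event are left as they are.
- Remove non-compliance as an automatic reason to end follow-up of a treated subject, and handle it through the per-protocol set in Section 11.5.3.
- Reconcile the mandatory wording of the list with the permissive wording in Section 6.3.
- Reconcile the replacement and evaluability sentence with the safety set and FAS in Sections 11.5.1 and 11.5.2.

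The cost is minor protocol wording and some effort to bring these subjects back, at visits that are already planned.

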## 6 SELECTION OF STUDY POPULATION

The intention is to enroll 70 patients who meet all eligibility criteria. Evaluation of the study participant inclusion/exclusion criteria will be based on the review of clinical medical records and documented patient interviews conducted by the investigator or under the direction of the investigator.

To be enrolled in the study, patients must meet ALL of the inclusion criteria and NONE of the exclusion criteria designated below.

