## **11.5 Analysis Data Sets**

### **11.5.1 Safety Analysis Set**

All subjects who received treatment will be included in the safety analysis set. The safety analysis set will be used for the summary and analyses of all safety endpoints.

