### **11.5.2 Full Analysis Set (FAS)**

The full analysis set (FAS) includes all eligible subjects who are enrolled in the study, received treatment and have at least one post treatment waist circumference measurement. The FAS will be used for the summary and analyses of the primary, secondary and exploratory endpoints.

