### **11.5.3 Per Protocol (PP) Analysis Set**

The per protocol (PP) analysis set will consist of all subjects from the FAS without any major protocol violations. The PP analysis set will be used for a sensitivity analysis of the primary endpoint.

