### **11.6.2 Disposition of Subjects/Data**

The numbers of subjects who were enrolled will be provided. A list of discontinued subjects together with the reasons for discontinuation will be presented.

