### **11.6.4 Efficacy Analyses**

All efficacy analyses will be performed on the FAS. All efficacy endpoints will be listed by subject and presented descriptively.

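### Section 10.2 declares non-completers not evaluable, an undefined term that conflicts with the FAS named for the primary endpoint and, taken literally, discards observed week-12 values

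*Combined protocol and SAP*

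**What the plan says.** All references are to the combined protocol and SAP.

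- **Section 10.1, definition of a completer:** "A subject will be considered to have completed the study if they complete the treatment as well as both follow up visits".
- **Section 10.2, rule for those who withdraw:** "Subjects who fail to complete the study will be replaced and will not be considered evaluable".
- **11.5.2 Full Analysis Set:** membership requires that the subject is eligible, enrolled, "received treatment and have at least one post treatment waist circumference measurement". The same section assigns the FAS to the primary, secondary and exploratory endpoints.
- **11.6.4 Efficacy Analyses:** "All efficacy analyses will be performed on the FAS". Presentation is descriptive, with listings by subject.
- **11.5.3 Per Protocol set:** "The PP analysis set will be used for a sensitivity analysis of the primary endpoint".
- **11.5.1 Safety Analysis Set:** "All subjects who received treatment will be included in the safety analysis set".
- **11.6.2 Disposition:** the number enrolled is to be given, and "A list of discontinued subjects together with the reasons for discontinuation will be presented".
- **Section 6:** "The intention is to enroll 70 patients who meet all eligibility criteria". Section 11.4 also gives 70 as the number to be enrolled.

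Section 11 does not define evaluability, does not use it in any analysis set, and does not mention replacement.

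**The concern.** Section 10.2 is an unqualified instruction about which subjects count, and it draws the line in a different place from the FAS. A site, data manager or analyst who followed it would exclude treated subjects whom section 11.5.2 includes. Some of them would have the week-12 waist measurement that is the primary endpoint.

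This matters more here than in a controlled trial. The study is open-label with one arm, so no comparison group shares the selection. If subjects with little waist reduction are the ones who skip a visit, a completers-only mean flatters the device. Section 10.2 also lets the investigators or the sponsor end participation for non-compliance. A subject removed that way becomes a non-completer, to be replaced and set aside. Nothing suggests this is intended, but the text permits it, and a reader of the results could not rule it out because no count of replaced subjects is planned.

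The exclusion also serves no stated analytic purpose. The plan already has a stricter population, the per-protocol set, with its own role as a sensitivity analysis.

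**Working it through.** **Step 1. Set the rules side by side.** Take treated, eligible subjects and classify them by the follow-up visits at which the waist was measured.

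| Week 6 | Week 12 | Completer (10.1) | Evaluable (10.2) | In FAS (11.5.2) | Has primary value (11.2.1) |
|---|---|---|---|---|---|
| yes | yes | yes | yes | yes | yes |
| yes | no | no | no | yes | no |
| no | yes | no | no | yes | yes |
| no | no | no | no | no | no |

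The rules disagree in rows 2 and 3. Row 2 affects the FAS count and the week-6 secondary summary. Only row 3 affects the week-12 mean.

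**Step 2. Is there a figure in the plan to reproduce?** No. Section 11.4 gives 70 without an effect, SD, alpha, power or dropout rate. Everything in steps 3 to 5 is therefore illustration under assumptions.

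**Step 3. Formula for the shift in the week-12 mean.** Let p be the share of subjects with a week-12 value who missed week 6, M their mean change, and C the mean change in those with both visits. The mean of all observed week-12 values is (1 - p)C + pM. The literal 10.2 reading gives C. The difference is

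C - [(1 - p)C + pM] = p(C - M).

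**Step 4. Assumed inputs.** Mean change -2.0 cm and SD 3 cm at both visits; correlation between week-6 and week-12 change 0.6 or 0.8; p = 3, 5 or 10% (about 2 to 7 of 70). The log-odds of missing week 6 are linear in week-6 change, with the intercept solved to give p. All subjects attend week 12, so the true mean of observed week-12 values is -2.0 cm. Negative entries mean that the 10.2 reading shows more reduction. Results are by numerical integration.

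| Odds ratio of missing per SD of worse week-6 change | Correlation | p = 3% | p = 5% | p = 10% |
|---|---|---|---|---|
| 1.00 (unrelated) | either | 0 | 0 | 0 |
| 1.35 (moderate) | 0.6 | -0.016 | -0.027 | -0.054 |
| 1.35 (moderate) | 0.8 | -0.022 | -0.036 | -0.071 |
| 1.82 (moderate) | 0.6 | -0.032 | -0.053 | -0.104 |
| 1.82 (moderate) | 0.8 | -0.043 | -0.071 | -0.139 |
| 4.48 (steep) | 0.6 | -0.073 | -0.117 | -0.219 |
| 4.48 (steep) | 0.8 | -0.097 | -0.156 | -0.292 |

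Hand check for odds ratio 1.82, correlation 0.8, p = 10%: M = -0.75 and C = -2.139, so p(C - M) = 0.10 x (-1.389) = -0.139 cm. The observed mean is 0.9 x (-2.139) + 0.1 x (-0.75) = -2.000, as it should be.

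As a share of the assumed 2.0 cm, the moderate cases run from 0.016/2 = 0.8% to 0.139/2 = 7.0%, and the steep ones from 0.073/2 = 3.6% to 0.292/2 = 14.6%. If good responders are the ones who skip week 6, the sign reverses.

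**Step 5. Scale.** With SD 3 cm and 70 values the standard error of the mean is 3/√70 = 0.36 cm, so even the largest entry is below one standard error.

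**Step 6. What the 70 counts.** Sections 6 and 11.4 speak of enrolment, and 10.2 adds replacement without linking the two. If replacement continued until 70 subjects had completed, enrolment would be 70/0.9 = 77.8, so 78, at an assumed 10% loss, and 70/0.8 = 87.5, so 88, at 20%. If replacements are counted within the 70, there would be fewer than 70 completers.

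**The case against.** The strongest reply is that section 11 settles the matter. Section 10.2 stands under subject withdrawal and names no analysis. Section 11.5.2 assigns the FAS to the primary endpoint, 11.6.4 repeats this for all efficacy analyses, and 11.5.3 confines the per-protocol set to a sensitivity analysis. An analyst would have to set aside two explicit statements to report completers only. This stands. A reader might infer from 10.2 that the plan leaves open which population decides the primary result; the documents do not support that, because they name the FAS. What the reply does not remove is the contrary instruction, which no sentence subordinates to section 11.

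Second, the effect is small and assumed. That also stands: it is zero if missing week 6 is unrelated to response, below one standard error in the worst case shown, and of uncertain sign. A reader might infer that the trial's result will be inflated; the documents give no dropout rate, SD or effect from which to conclude that.

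Third, a reader might attach to this point the larger bias that can arise when week-12 values themselves are missing. That does not belong here. A subject without a week-12 value contributes to the week-12 mean under neither rule, so such loss affects both readings alike.

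Fourth, losses will be partly visible through the discontinuation list and the by-subject listings. This is fair, but neither gives a count of replaced subjects or of waist values available at each visit.

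Finally, the safety set is not reduced by 10.2 as section 11.5.1 stands, since it takes in all treated subjects without condition.

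**Conclusion.** The point holds as a conflict in the text that should be corrected. The plan names the FAS for the primary endpoint, yet 10.2 labels as not evaluable two groups of treated subjects who belong to the FAS, using a term that is never defined or tied to an analysis set. One of those groups holds observed week-12 primary values, which a literal reading of 10.2 would discard in a study with no control arm.

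Confidence in the conflict is high, because it rests on the wording alone. The size is not established. Under the stated assumptions the week-12 mean shifts by 0 cm if missing week 6 is unrelated to response, about 0.02 to 0.14 cm under moderate dependence, and 0.07 to 0.29 cm under steep dependence, in either direction depending on who skips the visit. The case for changing the text does not depend on these figures: the clause can only remove data that the FAS is meant to keep.

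**What to change.** 1. In 10.2, strike the clause on evaluability. Alternatively, keep the replacement rule and state that replacement never removes a treated subject from the FAS or the safety set.
2. In 11.6.4, state that the week-12 primary summary is on the FAS and uses every observed week-12 value, whether or not week 6 was attended.
3. In section 6 and 11.4, state whether replacements are counted within the 70 enrolled or on top of them.
4. In 11.6.2, beside the discontinuation list, report the numbers treated, replaced, and with a waist value at each visit.

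The cost is a few sentences and one row of counts, with no new visits or data. No planned analysis is lost, because the per-protocol set remains as the stricter sensitivity population. The downside is that the reported mean may be slightly less favourable than a completers-only mean, and the number of week-12 values may differ from 70.
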